Official Title: Evaluation of a Novel Sutureless Drain Securement Device (K-Lock Device) and Comparison to Standard Suture-based Drain Securement Techniques

NCT05251753

IRB Approval Date: 11/09/2023

Study Title: Evaluation of a Novel Sutureless Drain Securement Device (K-Lock Device) and Comparison to Standard Suture-based Drain Securement Techniques

Principal Investigator: [name], MBA

Co-investigator(s): [name], [name]

Sponsor or funding source: Department of Plastic and Reconstructive Surgery

BACKGROUND, RATIONALE AND CONTEXT:

Surgical drains are used in a variety of surgical specialties and procedures. Drains are placed prior to closing the operative wound, and serve to allow draining of bodily fluids that would otherwise fill the new potential space created during an operation. Though there are various drain designs, the core structure of a drain involves tubing placed in the wound, exiting through the skin, and attached to a collection device that uses negative pressure to allow drainage of serosangunious or other fluids produced at the drain site.

To prevent the premature removal of surgical drains, the tubing is traditionally attached to the skin at the drain exit point using a suture. The suture is passed through the skin and then tied and wrapped around the tubing multiple times in a variety of patterns to hold the drain in place but not so tight as to occlude the tubing. When the suture is wrapped around the tubing multiple times over a distance, the technique is often referred to as the "Roman garter (RG) technique."

[figure not shown]

Figure 1. Patient Experience with Surgical Drains Compared to Pre-Operative Expectations. Patients were asked to use a sliding scale to characterize their experience with 0 = Experience Much Worse than Expected, 50 = Experience as Expected, 100 = Experience Much Better than Expected

[figure not shown]

Figure 2. Patient Drain Securement Experience. Patients were asked to rate comfort and pain at the drain insertion site with 0 = Experience Much Worse than Expected, 50 = Experience as Expected. 100 = Experience Much Better than Expected

Traditional suture-based fixation is known to cause significant patient discomfort, predominantly at the site of skin suture fixation, where any pull on the drain tubing is transmitted to a focal point on the skin. Over time, this can result in significant skin irritation, inflammation and pain, skin erosion, loosening of the drain, suture failure, and possibly even early, unintended loss of the drain. Early loss of a drain, in turn, can lead to complications of seroma and/or infected abscess. In a survey of 40 Wake Forest Plastic Surgery Patients with drains, patients asked were to rate their experience with surgical drains compared to their expectations on a sliding scale. The majority of patients reported experiences that were worse than or as expected (Figure 1). When specifically asked about irritation at the drain site, 33 of 40 patients rated comfort and pain as worse than

or as expected (Figure 2). With the known negative patient experiences associated with suture-based drain securement, there is a need for novel drain securement techniques and devices that can improve patient comfort and drain security.

The K-Lock® Device is a novel sutureless drain securement device that may improve patient experiences with surgical drains. The K-Lock Device is an FDA Class I device exempt from 510k requirements.

OBJECTIVES:

To evaluate the feasibility, safety and efficacy of a novel suture-less drain securement device (K-Lock) via direct comparison to suture-based techniques.

To evaluate patient satisfaction with their surgical drain sites post operatively.

DESIGN:

Randomized controlled trial

SETTING:

Academic Medical Center

SUBJECTS SELECTION CRITERIA:

Inclusion Criteria:

Age 18 or older

Patient of the Department of Plastic and Reconstructive Surgery

Able to sign English language Consent form

Undergoing any of the following procedures requiring placement of 2 or more drains (preferably bilateral) including:

- Breast reconstruction
- Bilateral Breast Reduction
- Abdominoplasty
- Body Contour surgery (e.g. panniculectomy, brachiplasty, thighplasty)

Exclusion Criteria:

Patients with unilateral drain placement Unable to sign English language consent form Allergy to Tegaderm Dressing Allergy to skin adhesives

SAMPLE SIZE:

We plan to enroll 40 patients allowing analysis of 80 (20 paired) drain sites: 40 prototype drain securement sites and 40 suture-based drain securement sites.

INTERVENTIONS AND INTERACTIONS:

Patients will be randomized to either A) left side K-Lock with right side suture-based technique or B) right side K-Lock with left side suture-based technique. Randomization will occur before study initiation with group A or group B being assigned to a study enrollment number.

Preoperatively:

The novel suture-less prototype device will be described and/or demonstrated to the patients, and the rationale for its development will be explained. They will have opportunity to ask questions and then they will be invited to participate in the study.

Written informed consent will be obtained.

Intraoperatively:

Surgical drains will be placed per the usual routine of the surgeon. However, prior to definitive fixation, the drains will be temporarily secured to the skin with a towel clamp and covered and/or positioned out of the way to allow for closure of surgical incisions. Definitive drain fixation will occur when all of the pertinent incisions are closed and dressed. At that time, each drain will be secured according to the randomization scheme.

The amount of **time it takes to secure and dress each drain will be recorded** using a time-stamped video (e.g. iphone). No identifying data/information will be recorded, only the zoomed field pertinent to drain securement. For the prototype drain securement device, the 'video clock' will be started when the device is passed to the surgeon and stopped when the device/dressing is attached in place. For the standard suture-based technique, the 'video clock' will be started when the suture is passed to the surgeon and will be stopped when the dressing has been placed and secured. Use of a Biopatch with the drain will be up to the surgeon's preference. The standard dressing for the suture-based techniques will include a split 4 x 4 dressing covered with a tegaderm. All dressing materials must be ready and available prior to handing the surgeon the suture/device.

Postoperatively:

The time until drain removal will be recorded for both groups.

On postoperative visit(s) on which a drain is removed, patients will complete a **survey** about their experience with the pertinent securement method/drain site.

Feasibility and **ease of use** of the novel drain device will be evaluated by evaluation of video recordings, qualitative feedback obtained from surgeons and/or O.R staff and nurses that handle and observe use of the device. Any failed application of the device will specifically be noted. In the event that a test device will need to be replaced for continued drain securement because the device has become loose or otherwise fouled, the replacement process will be performed by clinic staff using the IFU for such, and will be video recorded

Safety of the novel drain device will be evaluated by inspecting device sites for instances of skin irritation at each office visit and at the time of drain removal, including photographs of drain sites immediately before and after removal. It will also be assessed by feedback obtained in the patient surveys.

Postoperative review of patient charts will collect the following information up to 1 month from the removal of a subject's final drain:

- Date of drain removal (i.e. duration of drain)
- Accidental vs Planned drain removal
- Loosening of the drain
- Any need for new device/new suture material to secure drain
- Reinsertion of drain
- Patient calls to triage regarding drain issues/concerns and the estimated or actual time/effort devoted to each issue/concern by clinic staff
- Photos of the drain site at time of removal

As a follow-up to previous study activities, subjects will be contacted either by phone or at future clinic visits to gauge their interest in further participation. Subjects will be asked to have pictures taken of their drain sites and to fill out a survey to measure their satisfaction with their surgical drain sites further out from their procedures. Pictures will be attained at a scheduled research visit or a regular clinic visit if possible. A blinded evaluator will view the photos to assess in addition to the subject's self-reported outcomes. The tool the subjects will complete is the Patient and Observer Scar Assessment Scale (POSAS).

OUTCOME MEASURES:

Primary:

Feasibility

Secondary:

Safety

Satisfaction

ANALYTICAL PLAN:

Results will be analyzed initially using descriptive statistics. Comparison between groups will be done using chi square tests for proportions, and t-tests or ANOVA procedures for continuous variables. Regression analysis will be performed to identify independent outcome predictors. Other inferential statistical analysis will be conducted as appropriate.

HUMAN SUBJECTS PROTECTION:

Patient-identifying information will be limited to what is necessary to conduct retrospective analysis and longitudinal analysis of drain securement that is accurately linked to a given subject. MRN and DOB will be captured to ensure data about a subject's drain is accurately recorded during chart review. Other than the master 'linkage' file, patient names, DOB, and medical record numbers will be removed and subjects will be associated with an abstracted unique Study ID. Data will be stored electronically on the Wake Forest School of Medicine's secure REDCap server, a HIPAA-compliant web platform.

Information for each subject will be entered directly from EPIC to the secure REDCap database, so data will not be stored on portable storage devices (including thumb drives).

SUBJECT RECRUITMENT METHODS:

Patients will be identified by review of the departmental surgery schedule with study team members and identifying patients undergoing eligible surgical procedures.

For the follow-up portion, subjects will be contacted either by phone or at future clinic visits to gauge their interest in further participation.

INFORMED CONSENT:

Signed informed consent will be obtained from each subject. Study coordinators and/or study investigators will obtain consent at either clinic appointments or during preoperative intake. Subjects

being consented during preoperative intake will be contacted prior to their visit by phone and will undergo a phone screening.

CONFIDENTIALITY AND PRIVACY:

Confidentiality will be protected by collecting only information needed to conduct outcomes research and related research to improve breast reduction outcomes. All database data will be entered into the Wake Forest School of Medicine's secure REDCap server. To help ensure subject privacy and confidentiality, a linkage file will be maintained containing each patient's medical record number and unique REDCap ID. Patient names will not be maintained in this file. The linkage file will be stored separately from the data available to researchers and will be kept secure, with access limited to designated study personnel. Data access will be limited to study staff. Data and records will be kept locked and secured, with any computer data password protected. No reference to any individual participant will appear in reports, presentations, or publications that may arise from the study. Following data collection subject identifying information will be destroyed, within three years of closure of the study.

DATA AND SAFETY MONITORING:

The principal investigator will be responsible for the overall monitoring of the data and safety of study participants. The principal investigator will be assisted by other members of the study staff.

REPORTING OF UNANTICIPATED PROBLEMS, ADVERSE EVENTS OR DEVIATIONS:

Any unanticipated problems, serious and unexpected adverse events, deviations or protocol changes will be promptly reported by the principal investigator or designated member of the research team to the IRB and sponsor or appropriate government agency if appropriate.

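### Efficacy against suture is a stated objective with no listed outcome, and the named chi-square for proportions ignores the left/right randomisation within each patient

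*Combined protocol and SAP*

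**What the plan says.** **Objective.** The Objectives section commits to "To evaluate the feasibility, safety and efficacy of a novel suture-less drain securement device" and says this will be done "via direct comparison to suture-based techniques". The Background section gives the need as techniques "that can improve patient comfort and drain security", and warns that unintended early loss of a drain can lead to seroma or abscess.

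**Outcomes.** Outcome Measures lists feasibility as primary, and safety and satisfaction as secondary. Efficacy is not listed, and no variable is attached to any of the three headings.

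**Data collected.** Under Interventions and Interactions, the feasibility paragraph covers video review, staff feedback and two failure items. Both failure items concern the device only: "Any failed application of the device will specifically be noted", and the replacement procedure that begins "In the event that a test device will need to be replaced for continued drain securement". The chart-review list applies to both methods. It includes "Accidental vs Planned drain removal", loosening, need for a new device or new suture, and reinsertion.

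**Design and test.** "Patients will be randomized to either A) left side K-Lock with right side suture-based technique", or the mirror image. The Analytical Plan names chi-square tests for proportions and t-tests or ANOVA for continuous variables, as comparisons between groups. It closes with a general allowance for other suitable methods. No paired or clustered method is named.

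**The concern.** There are two gaps, and they meet at the same comparison.

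First, the objective has no endpoint. At least four chart-review items could be presented as efficacy. Unless one is fixed beforehand, the report can lead with whichever favours the device, and a reader cannot tell whether that happened.

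Second, the named test does not match the randomisation. Every patient contributes one side to each method, so the two proportions come from the same people. An ordinary chi-square treats the 40 device sides and 40 suture sides as unrelated. It uses only the two totals and gives the same p-value whether the losses fell in the same patients or in different ones. If losses on the two sides are positively correlated, the interval for the difference is wider than the data justify, and the benefit of the within-patient design is lost.

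**Working it through.** **1. The plan's own figure.** 40 patients × 2 sides = 80 sites, 40 per method. This reproduces the site counts in the Sample Size section. It also means 40 pairs, whereas the section describes the 80 sites as 20 paired. Everything below assumes 40 pairs.

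**2. Objective against outcome list.**

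| Objective | Listed outcome | Data that could serve |
|---|---|---|
| Feasibility | Primary | Videos, staff feedback, failed application |
| Safety | Secondary | Skin inspection, photographs, survey |
| Satisfaction | Secondary | Survey, scar scale |
| Efficacy against suture | None | Accidental removal, loosening, re-securement, reinsertion |

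The efficacy row has data but no designated outcome.

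**3. Inputs for the pairing check.** The documents give no loss rate, within-patient correlation, significance level or power. Assumed throughout: two-sided 5%; loss rates (suture vs device) of 20% vs 5%, 15% vs 5% and 10% vs 5%; within-patient correlation (phi) of 0, 0.2 and 0.4.

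**4. Standard error of the risk difference, 20% vs 5%.**

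- Unpaired: √[(p₁q₁ + p₂q₂)/n] = √[(0.16 + 0.0475)/40] = 0.0720.
- Paired: √[(p₁q₁ + p₂q₂ − 2·phi·√(p₁q₁p₂q₂))/n], where √(0.16 × 0.0475) = 0.0872.

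| phi | Paired SE | Unpaired SE too large by | 95% half-width, paired vs unpaired (points) |
|---|---|---|---|
| 0 | 0.0720 | 0% | 14.1 vs 14.1 |
| 0.2 | 0.0657 | 10% | 12.9 vs 14.1 |
| 0.4 | 0.0587 | 23% | 11.5 vs 14.1 |

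**5. Power and type I error (%).** Each entry is the summed multinomial probability of all tables that reject, over the four cells (loss on both sides, suture only, device only, neither). The both-sides cell is p₁p₂ + phi·√(p₁q₁p₂q₂). Values are for phi 0 / 0.2 / 0.4.

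| Suture vs device | Chi-square (uncorrected) | McNemar asymptotic | McNemar mid-p | McNemar exact |
|---|---|---|---|---|
| 20 vs 5, power | 57.4 / 58.0 / 58.4 | 51.4 / 61.8 / 79.5 | 50.4 / 58.6 / 69.6 | 39.3 / 45.7 / 53.9 |
| 15 vs 5, power | 34.9 / 32.8 / 29.8 | 29.5 / 36.3 / 47.0 | 27.1 / 30.5 / 34.4 | 18.0 / 19.4 / 20.5 |
| 10 vs 5, power | 14.6 / 11.6 / 8.4 | 12.3 / 13.9 / 15.1 | 8.8 / 8.5 / 7.5 | 4.4 / 3.8 / 2.9 |
| 20 vs 20, type I | 5.1 / 3.0 / 1.3 | 4.4 / 4.3 / 4.5 | 4.4 / 4.2 / 3.8 | 2.5 / 2.3 / 1.8 |
| 5 vs 5, type I | 4.3 / 2.4 / 1.0 | 4.1 / 3.1 / 1.8 | 1.5 / 0.9 / 0.4 | 0.4 / 0.2 / 0.1 |

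The chi-square falls below its nominal level as phi rises. At phi 0.2 and 0.4 the asymptotic McNemar test has more power than the chi-square at all three rate pairs. Mid-p gains from about phi 0.2 at 20% vs 5% and about 0.3 at 15% vs 5%, and does not gain at 10% vs 5% up to 0.4. The exact test has less power than the chi-square in every power cell shown.

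**6. An example that needs no assumed correlation.** Take losses in 8/40 suture sides and 2/40 device sides. The pooled rate is 10/80 = 0.125, so chi-square = 0.15²/(0.125 × 0.875 × 2/40) = 4.11, p = 0.043, whatever the pairing.

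| Patients with loss on both sides | Discordant pairs | (b − c)²/(b + c) | Asymptotic p | Mid-p | Paired Newcombe 95% CI (points) |
|---|---|---|---|---|---|
| 0 | 8 and 2 | 3.6 | 0.058 | 0.065 | −0.7 to 30.6 |
| 1 | 7 and 1 | 4.5 | 0.034 | 0.039 | 0.3 to 30.1 |
| 2 | 6 and 0 | 6.0 | 0.014 | 0.016 | 2.6 to 29.0 |

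The same totals support different conclusions, and the named test cannot tell them apart.

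**The case against.** **The chi-square error is mostly harmless.** At the null rates examined its type I error is at most 5.1%, and with independent sides it keeps its level and has somewhat more power. This stands. A reader might infer that the plan risks false claims of benefit. The calculations do not support that: under positive correlation the error is conservative.

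**Paired tests are not uniformly better.** This also stands. A reader might infer that any McNemar test gains power. The exact test does not in any scenario shown, and mid-p does not at 10% vs 5%. The firmer reason for pairing is a correct interval.

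**The plan is descriptive first and leaves room for other methods.** Feasibility is primary and no confirmatory efficacy claim is planned, which limits the weight of the point. But the closing allowance names no paired method and does not replace the chi-square that is named. The t-test and ANOVA wording could include paired forms; an ordinary chi-square cannot.

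**A two-method measure already exists.** Securement time is recorded on video for both methods, and feasibility is judged partly from video, so it would be too strong to say that feasibility involves no comparison with suture. Time to apply a device does not, however, show whether it holds the drain, and it is not designated as efficacy either.

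**Accidental removal is only one candidate.** Correct. Loosening, re-securement or reinsertion could also be defended. The documents do not make one item the only valid choice; they leave the choice open.

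**Drain duration.** From "The time until drain removal will be recorded for both groups" a reader might infer that durations will be pooled across planned and accidental removals. The plan commits to no such analysis, so this is not part of the point.

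**Conclusion.** Both parts hold. The missing efficacy outcome is plain from the text and depends on no assumed number. It is the weightier part, because a stated objective has no endpoint while several candidate items are collected.

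The mismatch between test and design is also clear, but its size is uncertain. At assumed rates of 20% vs 5% with 40 pairs, the unpaired standard error is too large by 0, 10 or 23% at phi 0, 0.2 or 0.4. The loss is of precision, not of protection against false positives, and it disappears if the sides are independent. These figures rest on assumed loss rates and correlations and on reading the sample size as 40 pairs. The change should be made, but nothing here invalidates the trial.

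**What to change.** 1. **Name the efficacy outcome before the data are analysed.** Accidental (unplanned) drain removal is closest to the Background's concern about unintended early drain loss. Score it yes/no per side. Eligibility allows more than two drains, so state that any accidental removal on a side counts for that side. Report loosening and need for a new device or suture separately.
2. **Analyse side-level proportions within patient.** For this and other side-level proportions, replace the chi-square. Make the paired risk difference with a 95% confidence interval (for example, paired Newcombe) the main result, supported by an asymptotic or mid-p McNemar test, not the exact one.
3. **Reconcile the sample size text.** 40 patients and 80 sites give 40 pairs, not 20.

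**Cost.** A few lines in the outcome list, Analytical Plan and Sample Size section. The items are already on the chart-review list, so no extra visits or patients are needed. The statistical price is somewhat lower power if the sides are independent: at 20% vs 5%, about 51% (asymptotic) or 50% (mid-p) against 57% for the uncorrected chi-square. Mid-p also has lower power at 10% vs 5% for phi from 0 to 0.4. With 40 pairs power is limited either way, so the result should be presented as an estimate with its interval, not as a superiority test.

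### Left and right drains need not match in body region or number, so the within-patient comparison loses precision and 40 + 40 sites is a floor rather than the count

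*Combined protocol and SAP*

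**What the plan says.** All references are to the combined protocol and SAP.

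- **Subjects Selection Criteria, inclusion:** "Undergoing any of the following procedures requiring placement of 2 or more drains (preferably bilateral) including". There is no upper limit on drains. Of the listed procedures, only breast reduction is specified as bilateral. Breast reconstruction, abdominoplasty and body contour surgery carry no such condition.
- **Subjects Selection Criteria, exclusion:** "Patients with unilateral drain placement".
- **Interventions and Interactions, allocation:** "Patients will be randomized to either A) left side K-Lock with right side suture-based technique or B) right side K-Lock with left side suture-based technique".
- **Interventions and Interactions, Intraoperatively:** "Surgical drains will be placed per the usual routine of the surgeon", and once the incisions are closed, "each drain will be secured according to the randomization scheme".
- **Sample Size:** "We plan to enroll 40 patients allowing analysis of 80 (20 paired) drain sites", described as "40 prototype drain securement sites and 40 suture-based drain securement sites".
- **Analytical Plan:** chi-square tests, t-tests or ANOVA, and regression. No paired or clustered method is named, and nothing is said about drain region or several drains on one side.

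**The concern.** The device question is answered by comparing a patient's two sides. That design gains most when the two drains are alike in everything except how they are secured. The criteria do not ensure this. A patient with a left breast drain and a right abdominal drain meets every written criterion, and so does a patient with two drains on one side and one on the other.

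In the first patient, the K-Lock minus suture difference contains a region difference as well as a device difference. Drain duration, loosening, skin irritation and comfort may all depend on where the drain exits and which wound it drains. In the second patient, the methods contribute different numbers of sites, and a patient with more drains counts for more in any comparison made drain by drain. The plan has no rule for choosing among, or averaging, several drains on one side.

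The two eligibility lines also disagree in wording, so screening staff could apply either one.

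**Working it through.** **1. Reproducing the stated count.** Input: 40 patients (Sample Size). With exactly one drain per side:

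- Sites: 40 × 2 = 80, as stated.
- Sites per method: 40 × 1 = 40, as stated.
- Left-right pairs: 40, against the stated 20. Twenty pairs would be only 20 × 2 = 40 sites.

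The 80 and the 40 + 40 reproduce, but only under one drain per side, which the plan does not require. The 20 pairs do not reproduce.

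**2. What the criteria deliver as written.** With the exclusion applied, each eligible patient has at least one drain per side, so 40 + 40 is the minimum before losses. Suppose a share of patients has one extra drain on one side (shares assumed, as the documents give none):

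| Share with one extra drain | Extra drains | Total sites | Range per method |
|---|---|---|---|
| 10% | 4 | 80 + 4 = 84 | 40 to 44 |
| 25% | 10 | 80 + 10 = 90 | 40 to 50 |
| 50% | 20 | 80 + 20 = 100 | 40 to 60 |

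The count can exceed the stated one even when the methods balance. If 20 patients had two drains and 20 had four, evenly split by side, the total would be 20 × 2 + 20 × 4 = 120, or 60 + 60.

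**3. Precision with unmatched regions.** Outcome: drain duration. Assumptions, none of them in the documents:

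- The SD of the paired difference in matched pairs is 3 days (variance 9).
- The two regions differ by d days, with d = 2 or 5.
- A share p of the 40 pairs is unmatched.

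In an unmatched pair the region difference enters as +d or −d according to the randomised side. It has mean zero and adds variance d². The variance of the mean difference is then (9 + p·d²)/40, and the standard error is multiplied by √((9 + p·d²)/9).

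| Unmatched pairs | p | d = 2 days | d = 5 days |
|---|---|---|---|
| 4 of 40 | 0.1 | √(9.4/9) = 1.02 | √(11.5/9) = 1.13 |
| 8 of 40 | 0.2 | √(9.8/9) = 1.04 | √(14/9) = 1.25 |
| 12 of 40 | 0.3 | √(10.2/9) = 1.06 | √(16.5/9) = 1.35 |

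With 8 unmatched pairs the standard error goes from √(9/40) = 0.474 days to √(9.8/40) = 0.495 days (d = 2) or √(14/40) = 0.592 days (d = 5). In matched pairs that is the precision of 40 × 9/9.8 ≈ 37 or 40 × 9/14 ≈ 26.

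**The case against.** Two stronger readings are tempting, and the documents support neither.

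- **A shortfall below 40 + 40.** Read alone, the inclusion line would admit a patient with both drains on one side, and pairs would be lost. The exclusion of unilateral placement rules this out. Eligibility as written allows only a surplus or an imbalance. A shortfall could come from changes during surgery or from missing data, but not from the criteria.
- **A biased device effect.** Within one unmatched patient, region and device cannot be separated. Across patients the side is randomised, so region falls on either method by chance. What remains is added variance, and a standard error computed from the observed within-patient differences would reflect it. Nor is the chance shift in the mean a second harm. For 8 unmatched pairs at 5 days it has SD 5 × √8/40 = 0.354 days, and √(0.592² − 0.474²) = 0.354 is the same variance again.

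Three further arguments carry weight. The primary outcome is feasibility, judged from videos, staff feedback and failed applications. Mixed regions have not been shown to harm that, and no power calculation depends on matching. The planned regression could include drain region, although the plan does not name it. Several drains per patient could be handled by an analysis rule without changing eligibility. For that reason additional drains should stay in a secondary analysis and not be discarded.

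None of this removes the conflict between the two eligibility lines, the absence of any rule on region or number, or a stated count that holds only with one drain per side.

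**Conclusion.** The point holds in limited form. The criteria contradict each other on bilateral placement, and nothing makes the two sides comparable in region or equal in number. The 40 + 40 sites are a floor before losses, and the 20 pairs do not fit 40 patients who each give a left-right comparison.

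The cost is precision and uneven patient weights. For drain duration with 8 of 40 pairs unmatched, the standard error rises by about 4% to 25%. The range rests on an assumed paired SD of 3 days and an assumed region difference of 2 to 5 days, and the unmatched share is also assumed. If unmatched patients are rare in this department, the loss is small. The absence of systematic bias further assumes that the allocated side does not influence where, or how many, drains are placed.

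**What to change.** 1. Replace the inclusion wording with: *at least one drain planned on each side of the body in the same anatomical region*. This agrees with the exclusion criterion and removes the contradiction.
2. Have the surgeon record one left-right index pair per patient, both drains in the same region, before the allocated side is disclosed. The timing matters because allocations are tied to enrolment numbers before the study starts, and a choice made with the side known could favour one method.
3. Base the main device comparison and the Sample Size statement on index pairs: 40 patients, 40 pairs, 40 + 40 sites before losses. Correct the 20 pairs accordingly.
4. Keep additional drains in safety reporting and in a secondary analysis that accounts for several drains per patient.

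The cost is one eligibility line, one case report form field and a corrected sentence under Sample Size. A few patients with unmatched drains become ineligible, and additional drains inform only the secondary analysis. How surgeons place drains does not change.

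### The protocol briefs patients on the new device and why it was developed, with no matching step for sutures, before they rate both methods unblinded

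*Combined protocol and SAP*

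**What the plan says.** The Preoperatively part of Interventions and Interactions sets out the briefing: "The novel suture-less prototype device will be described and/or demonstrated to the patients, and the rationale for its development will be explained". The next step fixes the order: "They will have opportunity to ask questions and then they will be invited to participate in the study". Written consent follows. No corresponding step for the suture technique appears there.

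The content of the rationale is not spelled out in that section. The Background is the only place where the protocol gives one. It says "Traditional suture-based fixation is known to cause significant patient discomfort", continues "With the known negative patient experiences associated with suture-based drain securement, there is a need for novel drain securement techniques and devices", and says that the K-Lock device "may improve patient experiences with surgical drains".

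Each patient then has K-Lock on one side and suture on the other, and only the side is randomised. At visits where a drain is removed, "patients will complete a survey about their experience with the pertinent securement method/drain site". The Objectives include "To evaluate patient satisfaction with their surgical drain sites post operatively". Outcome Measures lists feasibility as primary, with safety and satisfaction as secondary. Survey feedback also contributes to the safety assessment. The only blinded assessment described is the later review of photographs.

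**The concern.** Satisfaction is a subjective report by patients who can readily tell a suture from a sutureless device. Blinding them is not practical, so the way the two methods are introduced is the main remaining control over expectation. As written, the briefing describes one method and explains why it was developed. If that explanation follows the Background, it also indicates which answer the investigators hope for.

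Because each patient supplies both ratings, any such expectation falls directly on the within-patient contrast. A satisfaction difference, or a difference in survey-reported skin problems, could then be partly a product of the briefing. The plan describes no neutral script, no baseline measure of expectation and no analysis that addresses it, so the two sources could not be separated afterwards.

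**Working it through.** **The plan's own figure.** Sample Size gives 40 patients and 80 drain sites, described as 20 paired. 40 patients × 2 sites = 80 sites, which agrees. One site per method per patient gives 40 pairs, not 20. The point does not depend on this, so both counts are carried below.

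**Order of events, from the text.**

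| Step | New device | Suture | Where |
|---|---|---|---|
| Before invitation | Described and/or demonstrated, rationale explained | No step stated | Preoperatively |
| Rationale in the protocol | Possible improvement in experience | Known discomfort | Background |
| Allocation | One side, random | Other side | Interventions and Interactions |
| Patient rating | Survey at drain removal | Survey at drain removal | Postoperatively |
| Patient blinding | None described | None described | – |

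**Why randomising the side does not help.** Write the within-patient difference (K-Lock minus suture) as D = δ + β ± s + error. Here δ is the true device effect, β the shift due to expectation, and s a left–right effect whose sign depends on the allocation. With equal numbers in groups A and B, s averages out and the mean of D is δ + β. The shift β keeps the same sign in both groups, so neither randomisation nor a larger sample removes it.

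**Direction.** On an absolute comfort scale, a favourable expectation would tend to make β positive for K-Lock. The departmental survey in the Background used a different kind of scale: "Patients were asked to rate comfort and pain at the drain insertion site with 0 = Experience Much Worse than Expected", with 50 meaning as expected. Such a score behaves roughly like 50 + (experience − expectation). Raising the expectation for K-Lock by a and lowering it for suture by c then changes the contrast by −(a + c), which would hide a true advantage. Whether the trial survey uses this scale is not known, since the appendix is not available. The sign of β is therefore open.

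**Size (illustration only).** The documents give no expectation effect, standard deviation, significance level or sidedness. Assume a two-sided paired t-test at 0.05, δ = 0, and β = b standard deviations of the paired difference. The test statistic is then noncentral t with n − 1 degrees of freedom and noncentrality b√n. For b = 0.2 the noncentrality is 0.2 × √40 = 1.26, or 0.2 × √20 = 0.89.

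| b (assumed) | P(p < 0.05), 40 pairs | P(p < 0.05), 20 pairs |
|---|---|---|
| 0 | 5.0% | 5.0% |
| 0.1 | 9.5% | 7.1% |
| 0.2 | 23.5% | 13.6% |
| 0.3 | 45.7% | 24.7% |
| 0.4 | 69.4% | 39.7% |
| 0.5 | 86.9% | 56.5% |

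The table shows what a shift of a given size would do. It is not evidence that a shift of that size exists.

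**Reach.** Feasibility rests on video recordings, staff feedback and failed applications. Drain duration, accidental removal, loosening and re-securement come from chart review. Photographs in the follow-up are rated by a blinded evaluator. None of these is a patient's rating of the two methods. What remains exposed is patient-reported satisfaction and the survey component of safety, which supplements inspection and photographs of the sites.

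**The case against.** The strongest reply is that this is a recruitment conversation. Nobody can be invited to test a new device without hearing what it is and why it is being studied, and a patient with one sutured and one sutureless site will form expectations under any script. That stands. Only the part of the expectation due to an unbalanced briefing can be avoided, and the documents do not allow that part to be separated out.

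It is also fair that key materials are unseen. The consent form, the K-Lock information sheet and the patient survey are listed in the Appendix but are not available, and the consent form may describe both methods evenly. A reader might infer that patients are shown only the new device. The text does not say so: it allows description without demonstration, and the absence of sutures is silence in one section. A reader might also infer that patients are told sutures hurt. That takes the Background as the script, which is plausible but not stated, and even the Background is tentative about the device's benefit.

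These objections limit certainty. They do not remove the point, because the protocol makes the device briefing a step before the invitation and nowhere requires balance. An even-handed consent form read afterwards would not necessarily undo it.

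**Conclusion.** The point holds in a limited form. The protocol prescribes a pre-enrolment briefing on the new device and its rationale, states no counterpart for sutures, and then collects unblinded ratings of both methods from the same patients. Patient-reported satisfaction and survey-based safety feedback may partly reflect that briefing.

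Size and direction cannot be derived from the documents. The rejection rates above rest wholly on the assumed shift, the assumed test and the assumed 5% level. The point also assumes that the explanation resembles the Background and that the unseen documents do not already supply a balanced account.

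A reader might go further and conclude that any K-Lock advantage would be an artefact, or that the trial's main result is compromised. The documents support neither. The bias could run either way, and the primary feasibility outcome, the chart-review data and the blinded photo ratings are not affected. This is an inexpensive improvement to a secondary, patient-reported comparison.

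**What to change.** Replace the briefing sentence under Preoperatively with:

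> Both securement methods will be described and/or demonstrated in equal detail using a fixed, neutral script that gives the purpose of the study and the known risks of both methods, and states that it is not known which is more comfortable or secure.

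Align the information sheet and consent text with it. Keep the required disclosure of study purpose and of risks for both methods. Balance does not call for deleting every mention of suture discomfort or of why the device was developed, and doing so would conflict with risk disclosure.

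The cost is a minor amendment, a short script and a slightly less persuasive invitation, with no extra visits or staff. Any patients already enrolled will have had the present briefing, so the change cannot reach them and the satisfaction data would then mix two briefings.
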